11.4.1 Primary analysis

A. Percent change in Liver Function Tests including; Total serum bilirubin, direct serum bilirubin and Elevated Liver Enzymes (ALT, AST, ALP & GGT) after 6 months of treatment.

11.4.2 Secondary analysis:

- A. Improved degree of Steatosis from baseline (visit 1) to End of study between 3 treatment groups
- B. Improved quality of life between 3 treatment groups after 3 months (visit 4) and 6 months of treatment (End of study visit), using the RAND 36-Item Health Survey such as:
 - Physical functioning,
 - Role limitations due to physical health,
 - o Role limitations due to emotional problems,
 - Energy/fatigue,
 - Emotional well-being, social functioning,
 - o Pain
 - General health.
- C. Serious Adverse Events (SAEs)
- D. Adverse Events (AEs), including changes in any lab tests.
- E. AEs leading to permanent discontinuation of the study drug.

11.5 Interim analysis

No interim report.

12 Results:

- 12.1 Demographic Data and Vital Signs
- 12.2 Primary End Point:
- 12.3 Secondary End Point:
 - 12.3.1 Degree of Steatosis
 - 12.3.2 Quality of life (RAND 36-Item Health Survey)
 - 12.3.3 Safety Analysis

12.1 Demographic Data and vital signs

 Table 1
 Demographic Data and vital signs among treatment Groups

| | Group 1 | | | Group 2 | | | | n volue |
|--------------------------|---------|------|---------|---------|------|------|---------|-----------------|
| | Urso | UDCA | Placebo | p-value | Urso | UDCA | Placebo | p -value |
| Gender (male), N (%) | | | | | | | | |
| Age (Yrs.), mean (SD) | | | | | | | | |
| BMI, mean (SD) | | | | | | | | |
| Pulse, mean (SD) | | | | | | | | |
| Systolic, mean (SD) | | | | | | | | |
| Diastolic, mean (SD) | | | | | | | | |
| | | | | | | | | |
| | | | | | | | | |

Medical History

 Table 2
 Number and percent of medical history among treatment groups

| | Group 1 | | | n value | | p -value | | |
|----------------------|---------|------|---------|-----------------|------|-----------------|---------|-----------------|
| | Urso | UDCA | Placebo | p -value | Urso | UDCA | Placebo | p -value |
| N | | | | | | | | |
| Med history 1, N (%) | | | | | | | | |
| Med history 2, N (%) | | | | | | | | |
| Med history 3, N (%) | | | | | | | | |
| | | | | | | | | |
| | | | | | | | | |

12.2 Primary End Point

Table 3 Percent change of mean Total serum bilirubin at baseline and after 6 months of treatment

| Total serum bilirubin | Group 1 | | | n volue | | p -value | | |
|----------------------------------|---------|------|---------|-----------------|------|-----------------|---------|-----------------|
| | Urso | UDCA | Placebo | p -value | Urso | UDCA | Placebo | μ -value |
| V1 | | | | | | | | |
| V6 | | | | | | | | |
| % Change | | | | | | | | |
| p -value between V1 & V6 | | | | | | | | |
| p -value between 3 groups | | | | | | | | |

 Table 4
 Percent change of mean direct serum bilirubin at baseline and after 6 months of treatment

| direct serum bilirubin | Group 1 | | | n volvo | | p-value | | |
|---------------------------------|---------|------|---------|-----------------|------|---------|---------|---------|
| | Urso | UDCA | Placebo | p -value | Urso | UDCA | Placebo | ρ-value |
| V1 | | | | | | | | |
| V6 | | | | | | | | |
| % Change | | | | | | | | |
| p -value between V1 & V6 | | | | | | | | |
| p-value between 3 groups | | | - | | | | | |

 Table 5
 Percent change of mean ALT at baseline and after 6 months of treatment

| ALT | Group 1 | | | n volvo | | p -value | | |
|----------------------------------|---------|------|---------|-----------------|------|-----------------|---------|---------|
| | Urso | UDCA | Placebo | p -value | Urso | UDCA | Placebo | ρ-value |
| V1 | | | | | | | | |
| V6 | | | | | | | | |
| % Change | | | | | | | | |
| p -value between V1 & V6 | | | | | | | | |
| p -value between 3 groups | | - | - | | | | | |

Table 6 Percent change of mean AST at baseline and after 6 months of treatment

| AST | Group 1 | | | n volue | | p-value | | |
|----------------------------------|---------|------|---------|-----------------|------|---------|---------|---------|
| | Urso | UDCA | Placebo | p -value | Urso | UDCA | Placebo | μ-value |
| V1 | | | | | | | | |
| V6 | | | | | | | | |
| % Change | | | | | | | | |
| p -value between V1 & V6 | | | | | | | | |
| p -value between 3 groups | | | | | | | | |

 Table 7
 Percent change of mean ALP at baseline and after 6 months of treatment

| ALP | | Group 1 | | p -value | | p -value | | |
|----------------------------------|------|---------|---------|-----------------|------|-----------------|---------|---------|
| | Urso | UDCA | Placebo | p-value | Urso | UDCA | Placebo | ρ-value |
| V1 | | | | | | | | |
| V6 | | | | | | | | |
| % Change | | | | | | | | |
| p -value between V1 & V6 | | | | | | | | |
| p -value between 3 groups | | | | | | | | |

 Table 8
 Percent change of mean GGT at baseline and after 6 months of treatment

| GGT | | Group 1 | | p -value | | p -value | | |
|----------------------------------|------|---------|---------|-----------------|------|-----------------|---------|---------|
| | Urso | UDCA | Placebo | p-value | Urso | UDCA | Placebo | ρ-value |
| V1 | | | | | | | | |
| V6 | | | | | | | | |
| % Change | | | | | | | | |
| p -value between V1 & V6 | | | | | | | | |
| p -value between 3 groups | | | | | | | | |

12.3 Secondary End Point

12.3.1 Degree of Steatosis

Table 9 Percent change of mean degree of Steatosis at baseline and after 6 months of treatment

| Degree of Steatosis | Group 1 | | | p -value | | p -value | | |
|----------------------------------|---------|------|---------|-----------------|------|-----------------|---------|---------|
| | Urso | UDCA | Placebo | p-value | Urso | UDCA | Placebo | ρ-value |
| V1 | | | | | | | | |
| V6 | | | | | | | | |
| % Change | | | | | | | | |
| p -value between V1 & V6 | | | | | | | | |
| p -value between 3 groups | | | | | | | | |

12.3.2 Quality of life (RAND 36-Item Health Survey)

Table 10 Improved quality of life (Physical functioning, Role limitations due to physical health, Role limitations due to emotional problems, Energy/fatigue, Emotional well-being, social functioning, Pain and General health) from baseline and after 3 months of treatment

| | Group 1 | | | n value | | p -value | | |
|----------------------------------|---------|------|---------|-----------------|------|-----------------|---------|---------|
| | Urso | UDCA | Placebo | p -value | Urso | UDCA | Placebo | p-value |
| V1 | | | | | | | | |
| V4 | | | | | | | | |
| % Change | | | | | | | | |
| p -value between V1 & V3 | | | | | | | | |
| p -value between 3 groups | | | • | | | | | |

Table 11 Improved quality of life (Physical functioning, Role limitations due to physical health, Role limitations due to emotional problems, Energy/fatigue, Emotional well-being, social functioning, Pain and General health) from baseline and after 6 months of treatment

| | Group 1 | | | n valua | Group 2 | | | n value |
|---------------------------------|---------|------|---------|-----------------|---------|------|---------|-----------------|
| | Urso | UDCA | Placebo | p -value | Urso | UDCA | Placebo | p -value |
| V1 | | | | | | | | |
| V6 | | | | | | | | |
| % Change | | | | | | | | |
| p -value between V1 & V6 | | | | | | | | |
| p-value between 3 groups | | | | | | | | |

12.3.3 Safety Analysis

 Table 12
 Number and percent of Adverse Event among treatment groups

| | Group 1 | | | n valua | Group 2 | | | n value |
|--------------------------|---------|------|---------|-----------------|---------|------|---------|-----------------|
| | Urso | UDCA | Placebo | p -value | Urso | UDCA | Placebo | p -value |
| Total No of AE, N (%) | | | | | | | | |
| AE1, N (%) | | | | | | | | |
| AE2, N (%) | | | | | | | | |
| AE3, N (%) | | | | | | | | |
| | | | | | | | | |
| | | | | | | | | |

 Table 13
 Number and percent of Serious Adverse Event among treatment groups

| | Group 1 | | | - value | Group 2 | | | n volue |
|------------------|---------|------|---------|-----------------|---------|------|---------|-----------------|
| | Urso | UDCA | Placebo | p -value | Urso | UDCA | Placebo | p -value |
| Total SAE, N (%) | | | | | | | | |
| SAE1, N (%) | | | | | | | | |
| SAE2, N (%) | | | | | | | | |
| SAE3, N (%) | | | | | | | | |
| | | , | | | | | | |

> Concomitant Medication

 Table 14
 Number and percent of Concomitant medication among treatment groups

| | Group 1 | | | n valua | Group 2 | | | n value |
|----------------|---------|------|---------|-----------------|---------|------|---------|-----------------|
| | Urso | UDCA | Placebo | p -value | Urso | UDCA | Placebo | p -value |
| N | | | | | | | | |
| ConMed1, N (%) | | | | | | | | |
| ConMed2, N (%) | | | | | | | | |
| ConMed3, N (%) | | | | | | | | |
| | | | | | | | | |
| | | | | | | | | |

¹ - SF El Menshawe, AS Ahmed, LN Abdelaty, MA Aboseif. "Study of Hepatoprotective Effect of Silymarin and Ursodeoxycholic Acid in Chronic Hepatitis C Patients". Medicine Science 2014;3(4):1655-74

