- Improvement in Patients' quality of life (QoL) between 3 treatment groups after 3 months (visit 4) and 6 months of treatment (End of Study visit), using The RAND 36-Item Health Survey such as:
 - Physical functioning,
 - Role limitations due to physical health,
 - Role limitations due to emotional problems,
 - Energy/fatigue,
 - Emotional well-being, social functioning,
 - o Pain
 - General health
- Incidence of serious/non-serious adverse events, including changes in lab tests
- AEs leading to permanent discontinuation of the study drug.

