11.3 Statistical methods

This section provides specifications for preparation of final Statistical Analysis Plan (SAP), which will be issued prior to database lock. Any differences compared to this statistical section should be identified and documented in final SAP. Analysis will be done using SPSS version 21.

Categorical variables will be presented by number and percentage. Chi square test (or its subsidiaries) will be used to determine the p value. P -value <0.05 is considered significant.

Numerical Parametric variables will be presented by mean, SD and range. Paired ttest will be used to determine p-value between before and after treatment. Repeated measure ANOVA will be used to calculate significant effect for each group independently from baseline to end of treatment. One-way ANOVA test will be used to show and determine p-value and significance between 3 treatment groups at each point.

Numerical Non-Parametric variables will be presented by Median and interquartile range. Wilcoxon Sign Rank test will be used to determine p-value between before and after treatment. Friedman test will be used to calculate significant effect for each group independently from baseline to end of treatment. Kruskal-Wallis test will be used to show and determine p-value and significance between 3 treatment groups at each point.

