11.4 Analyses variables

The following variables will be analyzed by the overall sample, comparing study treatment versus 2 controls in the 2 groups: non-Cirrhotic liver and advanced Fibroitc & Cirrhotic liver.

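### Table 12 puts a percentage and a p-value on an adverse event count, and the overall safety comparison named in SAP 11.4 has no table

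*SAP*

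**What the plan says.** - **Endpoint (SAP 5.2).** The safety endpoint is "Incidence of serious/non-serious adverse events, including changes in lab tests". AEs leading to permanent discontinuation of study drug are listed as a further endpoint.
- **Population (SAP 11.2).** Safety is analysed in all patients who took at least one dose.
- **Methods (SAP 11.3).** "Categorical variables will be presented by number and percentage", "Chi square test (or its subsidiaries) will be used to determine the p value", and "P -value <0.05 is considered significant". No other test is given for data shown as N (%), and no rule says how a patient with several events is counted.
- **Scope (SAP 11.4).** "The following variables will be analyzed by the overall sample, comparing study treatment versus 2 controls in the 2 groups". The list that follows in 11.4.2 includes AEs, SAEs and AEs leading to discontinuation.
- **Table shells (SAP 12.3.3).** Table 12 is titled "Number and percent of Adverse Event among treatment groups" and opens with the row "Total No of AE, N" (%). Table 13 has the same layout for SAEs. Both show the three arms and a p-value inside Group 1 and inside Group 2, with no overall column. Neither has the N row that Tables 2 and 14 carry. No row or table covers AEs leading to discontinuation.

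**The concern.** Incidence is naturally a proportion of patients. The Table 12 total row is worded as a number of events, and a number of events has no natural percentage. A chi-square test treats each counted unit as independent, but several events from one patient are not. Repeated events are expected here: the protocol's AE form has several numbered rows per patient, and its instructions allow extra log pages. A p-value computed on that row could therefore flag a difference between arms that reflects a few patients with many events.

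The second part concerns what is compared. SAP 11.4 names the overall sample, but the shells hold only stratum comparisons. If the report follows the shells, the safety objective is answered twice in smaller samples and never in the whole trial.

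**Working it through.** The plan states no safety figure to reproduce: the shells are empty and no AE rate is given. The inputs from the documents are 3 arms, 99 patients per arm (SAP 7 and 8) and the 0.05 threshold (SAP 11.3). AE rates, variation between patients, incidences and stratum sizes are assumed below.

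**1. Chi-square on event totals across three equal arms.** Let φ be the variance divided by the mean of AEs per patient. With no true difference, the statistic behaves approximately as φ times a chi-square variable with 2 df. The critical value is 5.991, so

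false-positive rate ≈ exp(−5.991 / 2φ) = 0.05^(1/φ).

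The simulation used 20,000 null trials per row, 99 per arm and a mean of 0.8 AEs per patient, with Poisson counts for φ = 1 and negative binomial counts otherwise.

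| φ | Formula | Simulated, event totals | Simulated, patients with ≥1 AE |
|---|---|---|---|
| 1 (Poisson, equal rates) | 5.0% | 5.2% | 5.3% |
| 1.3 | 10.0% | 9.9% | 5.0% |
| 2 | 22.4% | 21.8% | 5.0% |
| 3 | 36.8% | 36.1% | 4.7% |

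At 50 per arm the event-total results are 4.9%, 9.9%, 22.1% and 36.1%. The problem is the same inside a stratum.

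**2. Events divided by patients, tested as a proportion.** This is the other way to fill an N (%) row with events. For a mean of m events per patient, the inflation factor becomes variance / [m(1 − m)]. At m = 0.3:
- Poisson counts: 0.3 / 0.21 = 1.43, so 0.05^(1/1.43) ≈ 12%.
- Negative binomial counts with φ = 1.3: 0.39 / 0.21 = 1.86, so 0.05^(1/1.86) ≈ 20%.

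At m = 1.0, at least one arm has more events than patients in about 85% of simulated trials. The percentage then passes 100 and the test is undefined.

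**3. Overall against stratum power.** Assume true AE incidences of 25%, 10% and 10%. The mean is 0.15. The non-centrality per patient per arm is (0.10² + 0.05² + 0.05²) / (0.15 × 0.85) = 0.015 / 0.1275 = 0.1176. Power is that of a non-central chi-square with 2 df.

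| Patients per arm | Non-centrality | Power, formula | Power, simulated |
|---|---|---|---|
| 99 (overall) | 11.65 | 87% | 85% |
| 66 | 7.76 | 70% | 68% |
| 50 | 5.88 | 58% | 56% |
| 33 | 3.88 | 40% | 40% |

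**4. Text against shells.** SAP 11.4 names the overall sample and the two fibrosis groups. Tables 12 and 13 provide the second and not the first.

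**The case against.** Three objections carry weight.

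First, SAP 11.3 assigns chi-square to categorical variables and never says that events are to be tested as independent units. N (%) looks like template wording: the same label on gender, medical history and concomitant medication plainly means patients. The endpoint is an incidence and the safety set is defined in patients. On that reading the individual AE rows and all of Table 13 are patient counts, and chi-square or an exact variant is valid. This stands for those rows. A reader might infer that every AE p-value in the plan is invalid; the documents do not support that. It does not rescue the total row of Table 12, which is labelled as a number of AEs.

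Second, a reader might infer that no overall safety comparison is planned. SAP 11.4 says otherwise: "The following variables will be analyzed by the overall sample". What is missing is the table. Nor is the layout peculiar to safety, since the efficacy shells also show only the two strata. SAP 11.3 foresees a final SAP before database lock, so the shells can still be completed.

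Third, the loss of power is smaller if both strata are read together. With about 50 per arm in each and 58% power per stratum, the chance that at least one is significant is 1 − 0.42² ≈ 82%, close to the overall figure. That comes at a combined false-positive rate of 1 − 0.95² = 9.75%, and it still gives no single estimate for the trial.

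**Conclusion.** The point holds in a limited form. One row, the total in Table 12, is worded as an event count with a percentage and a p-value. If filled that way, its p-value is not valid once patients have repeated events and differ in event rate. For a test of event totals the false-positive rate runs from about 5% in the benign Poisson case to about 36% at a variance-to-mean ratio of 3. Counting each patient once keeps it near 5% throughout. The remaining AE and SAE rows are not shown to be wrong; their unit and denominator are unstated, so two programmers could fill them differently.

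Separately, the overall comparison that SAP 11.4 names has no place in Tables 12 and 13. Under the assumed 25/10/10% incidences, that means about 40-70% power in a stratum of 33-66 per arm instead of 85-87% at 99 per arm. All these sizes depend on assumed rates, dispersion and stratum split, none of which the documents give. The matter is one of reporting and is minor: neither the design nor data collection is affected.

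**What to change.** In the final SAP:

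1. In Tables 12 and 13, define N (%) as patients with at least one event divided by treated patients, both in total and for each event term. Add an N row for the denominator. Test with chi-square, or an exact test where counts are small.
2. Report the total number of events as a separate line with no percentage and no p-value.
3. Add overall columns for the three arms, with risk differences and 95% confidence intervals, as the main safety comparison. Keep the two fibrosis groups as supportive, so that the shells agree with SAP 11.4.
4. Add a row for patients with an AE leading to permanent discontinuation of study drug. It is a listed endpoint with no output at present.

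The intervals in item 3 are good practice and do not correct an error in the text. The cost is a revision of table shells and SAP wording, with no change to the sample size, visits or data collected.
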